4.2 Objectives

4.2.1 Primary Objective

The primary research objective is to assess the safety of a new optimised virus vector for RPE gene replacement in the retina. Safety is defined as an ATIMP related:

- Reduction in visual acuity by 15 ETDRS letters or more
- Severe unresponsive inflammation (defined below)
- Infective endophthalmitis)
- Ocular malignancy
- Grade III or above non-ocular SUSAR (See Section 5.11.3)

Classification of severe unresponsive inflammation will be according to the SUN (standardisation of uveitis nomenclature) Working Group grading system (Am J Ophthalmol. 2005 Sep;140(3):50916.) i.e

- anterior chamber cells 3+ (26-50 cells in a field size of 1mm x 1-mm slit-beam), or
- anterior chamber flare 3+ (marked, iris and lens details hazy) or
- vitreous haze 3+ (Ophthalmology 1985; 92:467-71)

that fail to improve by 2 steps (or to grade 0) during a 6 week period.

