4.3.2.1 Dose escalation criteria and Dose Limiting Events

Dose escalation will be undertaken in adults, based on an escalation rule around Dose-Limiting Events (DLEs). An IDMC will review data from a minimum of 9 weeks of follow up from each cohort of 3 participants, before recommending the next dose to be assessed in a further cohort of participants.

A DLE is defined as any of the below occurring during the 9 weeks following administration, at least possibly related to the ATIMP, not surgery alone:

- Reduction in visual acuity by 15 ETDRS letters or more
- Severe unresponsive inflammation
- Infective endophthalmitis
- Ocular malignancy or
- Grade III or above non-ocular SUSAR (see section 5.11.3)

Severe unresponsive inflammation will be defined according to the Standardisation of Uveitis Nomenclature (SUN) Working Group grading system (Jabs *et Al.* 2005) i.e.

- anterior chamber cells 3+ (26-50 cells in a field size of 1mm x 1-mm slit-beam), or
- anterior chamber flare 3+ (marked, iris and lens details hazy), or
- vitreous haze 3+ (Ophthalmology 1985; 92:467-71)

that fails to improve by 2 steps (or to grade 0) during a 9-week period.

Review of safety data will be undertaken by the IDMC prior to each dose escalation. Children will be included at up to the highest safe vector dose recommended by the IDMC, once a safety profile has been established in adult participants.

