4.3.2.2 Dosing process

4.3.2.2.1 Cohort 1

Vector will first be administered at the lowest dose to 1 adult participant only. This participant will be monitored for signs of toxicity for a period of 9 weeks. If there is no DLE as defined above after a minimum of 9 weeks, vector will continue to be administered at the same dose to 2 further adult participants. In the event of a DLE in the first adult in the cohort, a discussion will be held with the IDMC to agree a plan of action for administering the ATIMP to further adults. The IDMC will review the data collected on this cohort of participants up to 9 weeks following vector administration to the 3rd participant.

4.3.2.2.2 Cohort 2

In the event that there is no DLE in any participant, the IDMC will recommend administering vector at the intermediate dose level to a single adult participant. If there is no dose-limiting toxicity after a minimum of 9 weeks, vector will continue to be administered at the same dose to 2 further adult participants. In the event of a DLE in the first adult in the cohort, a discussion will be held with the IDMC to agree a plan of action for administering the ATIMP to further adults. The IDMC will again review the data available on this next cohort of adult participants up to 9 weeks following vector administration to the 3rd participant.

4.3.2.2.3 Cohort 3

In the event that there is no DLE in any participant, the IDMC will recommend administering vector at the highest dose level to a single adult participant. If there is no DLE after a minimum of 9 weeks, vector will be administered at the same dose to 2 further adult participants. In the event of a DLE in the first adult in the cohort, a discussion will be held with the IDMC to agree a plan of action for administering the ATIMP to further adults.

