5.5 Outcomes

5.5.1 Primary Outcomes

The primary outcome is defined as any of the below occurring during the 9 weeks following administration, at least possibly related to the ATIMP, not surgery alone:

- Reduction in visual acuity by 15 ETDRS letters or more
- Severe unresponsive inflammation

- Infective endophthalmitis)
- Ocular malignancy
- Grade III or above non-ocular SUSAR. (See Section 5.11.3)

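### In 4.3.2.1 a 9-week non-response period sits inside a 9-week DLE window with no clock start or event date, so severe unresponsive inflammation may not be classifiable by week 9

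*Combined protocol and SAP*

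**What the plan says.** Section 4.3.2.1 sets the window: "A DLE is defined as any of the below occurring during the 9 weeks following administration". One listed event is severe unresponsive inflammation, defined there as 3+ anterior chamber cells, flare or vitreous haze "that fails to improve by 2 steps (or to grade 0) during a 9-week period".

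The same 9 weeks govern the dose decisions. Section 4.3.2.1 states: "An IDMC will review data from a minimum of 9 weeks of follow up from each cohort of 3 participants". For the first participant in cohort 1, section 4.3.2.2.1 states: "If there is no DLE as defined above after a minimum of 9 weeks, vector will continue to be administered at the same dose". Similar first-participant gates apply to cohorts 2 and 3 and to the first child (4.3.2.2.2, 4.3.2.2.3, 4.3.2.2.5). Table 1 in 4.3.2.2.4 runs on the number of DLEs.

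The primary outcome in 5.5.1 uses the same list and window, "any of the below occurring during the 9 weeks following administration, at least possibly related to the ATIMP", and 5.10.4.2 repeats it. Neither section restates the definition of severe unresponsive inflammation. The primary objective in 4.2.1 does define it, with a different period: 3+ signs "that fail to improve by 2 steps (or to grade 0) during a 6 week period".

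None of these sections says when the non-response period starts. None says whether the event is dated at onset or when the definition is met.

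**The concern.** A persistence criterion as long as the window that contains it leaves no room for onset, unless the clock or the dating rule is specified. Take an eye that reaches 3+ at week 1 and is unimproved at weeks 2, 4, 6 and 9. Whether it is a DLE at the week-9 gate depends on a reading that the protocol leaves open.

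Two uses are affected. The first is dose escalation, where gates and Table 1 depend on whether a DLE has been recorded. The second is the primary analysis, where 5.10.4.2 plans a 95% confidence bound on the event rate in up to 15 participants at the maximum tolerated dose. Section 4.1.1 treats intraocular inflammation and immune responses at the top dose of earlier trials as a sign of dose-limiting toxicity, so this item needs a workable definition.

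**Working it through.** **Inputs.** DLE and primary-outcome window: 9 weeks (4.3.2.1, 5.5.1, 5.10.4.2). Non-response period: 9 weeks = 63 days (4.3.2.1) or 6 weeks = 42 days (4.2.1). Gates and cohort reviews: minimum 9 weeks (4.3.2.1, 4.3.2.2). Visits: Table 2 in 5.6. The revision history for V5 explains the window as the 8-week steroid course plus one week: 8 + 1 = 9 weeks = 63 days, which reproduces the stated figure.

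**Reading A: clock starts at onset, event dated when the definition is met.** Completion day = onset day + non-response period. Latest admissible onset = 63 − period.

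| Onset | Completion, 9-week period | Completion, 6-week period |
|---|---|---|
| Day 1 | 64 | 43 |
| Day 3 | 66 | 45 |
| Week 1 (day 7) | 70 | 49 |
| Week 2 (day 14) | 77 | 56 |
| Week 4 (day 28) | 91 | 70 |
| Week 6 (day 42) | 105 | 84 |

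With 9 weeks the latest admissible onset is 63 − 63 = day 0, so no onset from day 1 qualifies. With 6 weeks it is 63 − 42 = day 21: onsets to week 2 qualify, but those at weeks 4 and 6 do not. Adopting 6 weeks throughout would therefore shrink the problem without removing it.

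**Reading B: clock starts at onset, event dated at onset.** Any onset by day 63 belongs to the window, and a 9-week period is complete by 63 + 63 = day 126, before the week-24 visit (day 168). The final analysis could capture it. At a day-63 gate it is still unconfirmed. At the cohort review the first participant has at least 63 + 63 = 126 days of follow-up, because the next two are dosed only after 9 weeks, so that case can be settled. The most recently dosed participant may have only 63 days, so that case cannot.

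**Reading C: the 9-week period is the post-dosing window itself.** Inflammation at 3+ and unimproved by week 9 is then a DLE, and the item works in time. Its side effect is that inflammation first seen at week 8 (day 56) has 63 − 56 = 7 days to respond before being classed as unresponsive.

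**Size for the primary outcome (hypothetical).** Suppose one of 15 participants had such inflammation. Under the 4.3.2.1 definition with Reading A, the result is 0/15, with exact two-sided 95% upper limit 1 − 0.025^(1/15) = 21.8%. If the event counts, the result is 1/15, with upper limit 31.9%. Under the 6-week definition, the week-1 example above completes on day 49 and counts.

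**Size for escalation (hypothetical).** The documents give no rate for this event. Assume true rates p of 10, 20, 30 and 40%, no other DLEs and mechanical use of Table 1. The chance that a dose level passes is (1−p)³ + 3p(1−p)² × (1−p)³ = 91, 71, 49 and 31% if these events count, and 100% if Reading A keeps them all out.

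**The case against.** The strongest reply is that Reading C was intended. The V5 entry says that the period for considering DLEs was lengthened from 6 to 9 weeks to span the steroid course plus a week, which fits one shared period. That is plausible, but 4.3.2.1 refers to a 9-week period without tying it to dosing, and 4.2.1 still says 6 weeks.

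Second, 5.5.1 and 5.10.4.2 contain no 9-week non-response period, so the primary outcome may rest on the 6 weeks in 4.2.1. This stands. A reader might infer that the primary analysis must record zero inflammation events. The documents do not support that: it requires the 4.3.2.1 definition and completion dating together.

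Third, the committee does not see only a DLE count. It reviews safety data before each escalation (4.3.2.1, 5.11.1) and may ask for more participants at a dose (4.3.1, 4.3.2.2.4). Safety events are reviewed promptly (5.11.3.2), all adverse events are recorded (5.11.3.5), and the gates are minimums. A 15-letter acuity loss is a separate DLE that may catch some of these eyes. All of this stands as partial mitigation, so it would be wrong to infer that dosing would proceed as though persistent inflammation had not happened. It does not make the definition workable.

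Fourth, the known cases are not cases of this event. The 3 of 12 in the earlier trial were transient, and the minority in this trial responded to further corticosteroids (4.1.5.1). Section 4.1.1 likewise reports resolution in all earlier instances. They give no rate for severe unresponsive inflammation and do not show that any event has been missed.

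**Conclusion.** The point holds as an unresolved definition in a stated decision rule. A reader might go further and infer that inflammation starting after dosing can never count. That follows only under Reading A with the 9-week period. Under Reading B the fault is late classification: the event belongs to the window but is unconfirmed at a 9-week gate, and at the cohort review for the last participant dosed. Under Reading C there is no timing conflict, but the text does not state that reading.

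For the primary outcome the consequence is conditional. With the 6-week period and completion dating, onsets after day 21 are lost. The change in upper limit from 31.9% to 21.8% is an illustration under Reading A and the 4.3.2.1 definition, not an expected bias. The escalation percentages rest on assumed rates.

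**What to change.** Reconcile the non-response periods in 4.2.1 and 4.3.2.1 with the 9-week DLE window and with the 9-week gates and reviews in 4.3.2.1 and 4.3.2.2. State when the non-response clock starts and how the event is dated. The choice of clinical period, and the handling of unresolved cases at dose decisions, belong to the sponsor and the IDMC. This review does not propose either.

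For the final analysis, write the dating rule into 5.5.1 and 5.10.4.2, so that inflammation first reaching 3+ within the 9 weeks is not lost because its non-response is confirmed later. Section 5.4.2.3 already has inflammation graded by slit lamp at each time point, and the week 9, 12 and 24 visits exist, so no new assessment is needed.

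The cost is protocol and analysis-plan wording. The small downside is that a case may be classified only after week 9.

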4.3.2.2 Dosing process

4.3.2.2.1 Cohort 1

Vector will first be administered at the lowest dose to 1 adult participant only. This participant will be monitored for signs of toxicity for a period of 9 weeks. If there is no DLE as defined above after a minimum of 9 weeks, vector will continue to be administered at the same dose to 2 further adult participants. In the event of a DLE in the first adult in the cohort, a discussion will be held with the IDMC to agree a plan of action for administering the ATIMP to further adults. The IDMC will review the data collected on this cohort of participants up to 9 weeks following vector administration to the 3rd participant.

4.3.2.2.2 Cohort 2

In the event that there is no DLE in any participant, the IDMC will recommend administering vector at the intermediate dose level to a single adult participant. If there is no dose-limiting toxicity after a minimum of 9 weeks, vector will continue to be administered at the same dose to 2 further adult participants. In the event of a DLE in the first adult in the cohort, a discussion will be held with the IDMC to agree a plan of action for administering the ATIMP to further adults. The IDMC will again review the data available on this next cohort of adult participants up to 9 weeks following vector administration to the 3rd participant.

4.3.2.2.3 Cohort 3

In the event that there is no DLE in any participant, the IDMC will recommend administering vector at the highest dose level to a single adult participant. If there is no DLE after a minimum of 9 weeks, vector will be administered at the same dose to 2 further adult participants. In the event of a DLE in the first adult in the cohort, a discussion will be held with the IDMC to agree a plan of action for administering the ATIMP to further adults.

4.3.2.2.4 Additional considerations

In the event of a DLE in one of the 3 participants at any given dose, the cohort will be expanded at the same dose level. The IDMC will review the safety data and confirm that additional participants may be treated at this dose. The IDMC may recommend that the same dose of ATIMP is administered to additional participants. The dose escalation will continue until 3 participants have been either administered the highest dose without any DLEs, or until at least 2 participants among a cohort of 3 to 6 participants experience DLEs (i.e., $\geq 33\%$ of participants with a DLE at that dose level), in which case the recommended dose will be the level below this toxic dose. In the event that 1 or 2 DLEs are seen at the first dose level, the IDMC may recommend administering a lower dose to that described in the protocol to a cohort of participants.

Table 1: Dose escalation table

Number of DLEs		Action	Details
Low dose			
Participants 1-3	Participants 4-6		
0/3		Increase	Give intermediate dose to next cohort of participants
1/3		Remain	Give low dose to another cohort of participants (Pt 4-6)
≥ 2/3		Stop	MTD not found. Consider lower dose
	≤ 1/6	Increase/stop	Has higher dose been tried? No: Give intermediate dose to next cohort of participants Yes: MTD found – low dose
	≥ 2/6	Stop	MTD not found. Consider lower dose
Intermediate dose			
Participants 1-3	Participants 4-6	Action	Details
0/3		Increase	Give high dose to next cohort of participants
1/3		Remain	Give intermediate dose to participants 4-6
≥ 2/3		Decrease/stop	Give low dose to 3 more participants. If 6 participants already had low dose, stop. MTD found – low dose.
	≤ 1/6	Increase/stop	Has higher dose been tried? No: Give high dose to participants 1-3 Yes: MTD found – intermediate dose
	≥ 2/6	Decrease/stop	Give low dose to participants 4-6. If 6 participants already had low dose, stop. MTD found – low dose
High dose			
Participants 1-3	Participants 4-6	Action	Details
0/3		Remain	MTD found – give high dose to participants in confirmation phase
1/3		Remain	Give high dose to participants 4-6
≥ 2/3		Decrease/stop	Give intermediate dose to participants 4-6. If 6 participants already had intermediate dose, stop. MTD found – intermediate dose
	1/6	Stop	MTD found – high dose
	≥ 2/6	Decrease/Stop	Give intermediate dose to participants 4-6. If 6 participants already had intermediate dose, stop. MTD found – intermediate dose

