
4.3.2 IMP administration Review and Dose Escalation Criteria and Process

Up to 18 adult participants (as defined in Section 4.3.1) will be administered 1 of 3 doses according to the dose-escalation criteria:

MGT003, Gene Therapy Trial for LCA OPTIRPE65

- | | |
|----------------------|-----------------------------------|
| 1) low dose | 1mL at 1.0×10^{11} vg/mL |
| 2) intermediate dose | 1mL at 3.0×10^{11} vg/mL |
| 3) high dose | 1mL at 1.0×10^{12} vg/mL |

Once a maximal tolerated dose is established, up to a further 9 participants aged 3 or above will continue to be administered vector up to the highest dose observed to be well tolerated in adults.

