5.10.4.2 Statistical Methods – Primary Outcome Analysis

The primary outcome is safety of subretinal administration of the ATIMP, defined as any of the below occurring during the 9 weeks following administration, at least possibly related to the ATIMP, not surgery alone:

- Reduction in visual acuity by 15 ETDRS letters or more
- Severe unresponsive inflammation
- Infective endophthalmitis
- Ocular malignancy
- Grade III or above non-ocular SUSAR (See Section 5.11).

The number of DLEs at each dose level will be summarised by cohort and overall.

It is anticipated that the vector will be administered at the MTD in up to 15 participants (6 adults in the dose escalation phase and up to 9 further adults and children in the confirmatory safety phase). Safety data relating to these participants will allow estimation of an upper bound for the true event rate through a 95% confidence interval.

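### Table 1 records 0/3 or 1/6 DLEs at the highest planned dose as an MTD found, where the data would support only: highest planned dose tolerated, MTD not reached

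*Combined protocol and SAP*

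**What the plan says.** Section 4.3.2 plans three dose levels for adults and none above the third. With 0/3 DLEs at the low dose, Table 1 (section 4.3.2.2.4) moves on: "Give intermediate dose to next cohort of participants". With 0/3 at the intermediate dose it does the same: "Give high dose to next cohort of participants". With 0/3 at the high dose it reads "MTD found – give high dose to participants in confirmation phase". With 1/6 at the high dose it again records an MTD.

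The prose above the table ends escalation in one of two ways. One is "until 3 participants have been either administered the highest dose without any DLEs"; the sentence does not call that result an MTD. The other is that "at least 2 participants among a cohort of 3 to 6 participants experience DLEs", "in which case the recommended dose will be the level below this toxic dose".

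Other sections then rely on an MTD:
- Section 4.3.2 opens the next stage with "Once a maximal tolerated dose is established, up to a further 9 participants aged 3 or above".
- Section 5.10.4.2 says "It is anticipated that the vector will be administered at the MTD in up to 15 participants" and plans a 95% confidence interval from those participants.
- Sections 4.3.1, 4.3.2.2.5 and 5.3.1.2 (criterion 1) tie the dosing and enrolment of children to an agreed or identified MTD in adults.

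The abbreviation list expands MTD, but no section defines it.

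**The concern.** Table 1 uses one label for two different findings. At the low and intermediate doses, an MTD is a tolerated dose with a failed dose above it. At the high dose it is the last dose on the list, with nothing known about any dose above. Every way of passing the high dose is labelled as a found MTD. The only *not found* outcome sits at the low dose and means too much toxicity, so the table cannot record that no limit was reached.

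What is at stake is the wording of the conclusion. An MTD equal to the top planned dose could be taken to mean that toxicity begins just above it, when the value was set by the planned range. The protocol's own Background (section 4.1.1) encourages that reading: it describes dose-limiting toxicity in an earlier trial and says that a maximal tolerated dose was identified there.

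**Working it through.** **1. Reproduce the plan's figures.** Three doses with at most 6 adults each give 3 × 6 = 18, and 18 + 9 = 27, as in section 5.7. The stopping count of 2 in 6 is 33%, as in section 4.3.2.2.4. The plan gives no probability of declaring an MTD.

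**2. Where Table 1 names an MTD.**

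| Dose named | Condition | Has a higher dose failed? |
|---|---|---|
| Low | At most 1/6, and a higher dose already tried; or at least 2 DLEs at intermediate with 6 already treated at low | Yes |
| Intermediate | At most 1/6, and a higher dose already tried; or at least 2 DLEs at high with 6 already treated at intermediate | Yes |
| High | 0/3 | No; none is planned |
| High | 1/6 | No; none is planned |

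A lower dose counts as having a higher dose already tried only when the trial has come back down after at least 2 DLEs. So the first two rows are bracketed by an observed failure and the last two are not.

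**3. A vector with no DLEs at any dose.** Only one path exists: 0/3 at low, 0/3 at intermediate, 0/3 at high, using 9 adults. It ends in the high-dose MTD cell, so the label is applied with probability 1 if the table is followed.

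**4. Low but non-zero DLE rates.** Assume the same true rate p at every dose, with q = 1 − p; these rates are assumptions, not figures from the plan. The chance of passing one level is q³ + 3pq² × q³, and the chance of an MTD recorded at the high dose is the cube of that.

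| p | Pass one level | MTD recorded at high dose |
|---|---|---|
| 0 | 1 | 100% |
| 1% | 0.9703 + 0.0285 = 0.9988 | 99.6% |
| 2% | 0.9412 + 0.0542 = 0.9954 | 98.6% |
| 5% | 0.8574 + 0.1161 = 0.9734 | 92.2% |
| 10% | 0.7290 + 0.1771 = 0.9061 | 74.4% |

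Enumerating every path through Table 1, including the downward steps, gives the same results.

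**5. What 0/3 supports.** The one-sided 95% upper limit for the DLE rate is 1 − 0.05^(1/3) = 0.63. At a true rate of 33%, the chance of 0/3 is 0.67³ = 0.30. So 0/3 shows that the dose passed the protocol's rule. It does not locate a limit above that dose, and it bounds the rate at the dose itself only loosely.

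**6. After relabelling.** For a vector with zero DLE risk, the probability of recording a located MTD falls from 1 to 0. The path, the dose carried forward and the numbers treated stay the same.

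**The case against.** The best defence is that the protocol uses MTD operationally, to mean the highest dose found tolerable within the range studied. Section 4.3.2 treats an established MTD and the highest dose well tolerated in adults as the same thing in one sentence. Sections 4.3.2.1 and 4.3.2.2.5 speak of the highest safe or agreed dose. On that meaning, 0/3 at the top dose does identify the dose. This shows that sounder wording is already in the protocol, and it limits the harm. It does not remove the problem, because the low- and intermediate-dose rows of Table 1 require a failed higher dose and no section defines the term otherwise.

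Stronger readings are tempting, and the documents do not support them:

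- *That the main result of the trial is wrong.* The MTD is not a listed objective or outcome (sections 4.2 and 5.5). The primary outcome is a set of safety events, and DLE counts are to be summarised at each dose, so readers would see the zeros.
- *That the 95% bound in section 5.10.4.2 is distorted.* It depends on events and numbers at the dose, which the label does not alter. On the 0/3 path the number at that dose is at most 3 + 9 = 12 unless the IDMC adds participants, against 6 + 9 = 15. The section says up to 15, so 12 falls within it. With zero events the two-sided upper limits would be 1 − 0.025^(1/12) = 26.5% and 1 − 0.025^(1/15) = 21.8%. Relabelling affects neither.
- *That the final report is certain to claim an MTD.* The IDMC agrees the MTD (section 4.3.1), and section 5.10.4.1 defers to an analysis plan still to be written. But nothing directs either of them to say that the MTD was not reached.
- *That the percentages are error rates.* They are the chances that a low-toxicity product passes all three levels, which the design should allow. Above 0%, they include paths on which a DLE occurred.

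**Conclusion.** The point holds as a labelling error in Table 1. With 0/3 or 1/6 DLEs at the high dose, the table states a conclusion that the data cannot support, and it offers no outcome for an MTD that was not reached. For a vector with no DLEs at any dose this follows with certainty, provided that the table is followed as written and no background event is judged at least possibly related to the product. The consequence is confined to the stated conclusion. No participant is treated differently, no estimate is biased, and the dose taken forward and the sample size stay as they are. This is a minor point, worth correcting because it costs so little.

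**What to change.** In Table 1, relabel the high-dose 0/3 and 1/6 outcomes *highest planned dose tolerated; MTD not reached*. Keep *MTD found* for cases where a higher dose met the stopping count, and report the result in those terms.

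Two table cells are not enough. Sections 4.3.1, 4.3.2, 4.3.2.2.5, 5.3.1.2 (criterion 1) and 5.10.4.2 all rely on an MTD that has been agreed, established or identified. If they were left unedited, a *not reached* label would conflict with the conditions for enrolling and dosing children. Each passage must be reconciled so that it still points to the same IDMC-agreed dose as now. No dose, escalation step or enrolment rule is proposed or changed.

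The cost is two cells and a short edit in five sections. The one downside is that the report may have to state that no MTD was identified.
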